Optimal treatment duration for acute VTE and the secondary prevention of recurrent VTE is not definitively known. The two terms “acute treatment” and “secondary prevention” are not precisely defined and might overlap. Current guidelines recommend treatment for 3 months over shorter treatment durations [[P12-01518](#), [P14-16368](#)]. An extended duration of anticoagulation treatment should be considered for those patients with the greatest risk of VTE recurrence, i.e., those with an unprovoked DVT and/or PE; recurrent VTE, co-morbidities, such as cancer, chronic inflammation of the peripheral veins, and a strong genetic pre-disposition to thrombosis.

For patients with a chronic risk of recurrent VTE, there is evidence that when oral anticoagulation therapy is stopped, the risk of recurrence will increase to pre-treatment levels [[P08-08095](#), [R09-4888](#)]. Therefore, the decision to continue treatment for prevention of recurrent VTE must consider the risk factors for recurrence as well as any risk factors for bleeding. The risk of bleeding increases in patients with a prior history of bleeding events, the presence of certain co-morbidities (e.g., gastrointestinal ulceration, inflammation or malignancy or other metabolic disorders that might alter hemostasis such as cirrhosis or chronic renal disease or concomitant medications that alter hemostasis (i.e. antiplatelet agents)). These risks must be reviewed periodically, and therefore, treatment decisions should be individualized and periodically reviewed.

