#### **9.7.2.1 Main analyses**

For Objective 1:

Baseline patient demographics and disease characteristics, including information regarding the index VTE event, medical history, concomitant therapies, and laboratory data as specified in [Section 9.3.1](#), will be summarized descriptively for all eligible patients overall and by anticoagulation treatment at baseline. The analysis will be repeated by region and by additional relevant patient attributes.

Patterns of anticoagulation treatment at baseline will be described overall, by region, and by additional relevant patient attributes.

For Objective 2:

Patient demographics and disease characteristics at baseline as described above for Objective 1 will be summarized descriptively for all eligible patients by their initial anticoagulation treatment (i.e. dabigatran etexilate or VKA). This analysis will be repeated by region and by additional relevant patient attributes.

Given the observational nature of this study, patients in the dabigatran etexilate and VKA groups may differ with regard to important baseline demographics and disease characteristics. When the target sample size is reached, propensity scores that estimate the probabilities that patients would be initiated on dabigatran etexilate will be calculated using a logistic regression model that considers variables that are risk factors for the occurrence of VTE or bleeding events or affect the choice of anticoagulation treatment (details of the model will be provided in the SEAP). Overlap of propensity scores between the dabigatran etexilate and VKA groups will be examined to assess the comparability of the two patient populations, and to estimate the loss of patients from the comparative analysis if trimming or matching is to be performed.

The primary safety and effectiveness outcomes will be analyzed for dabigatran etexilate patients in comparison to VKA patients using Cox proportional hazards models. Confounding will be controlled for using appropriate methods, including adjustment of covariates in the Cox regression model, trimming of extreme observations, and/or propensity score matching, based on the evaluation of the comparability of dabigatran etexilate and VKA patients (i.e. overlap of propensity scores) as described above. Details of the analytical methods and the selection rules of the appropriate analysis strategy will be provided in the SEAP.

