6. GENERAL ANALYSIS DEFINITIONS

6.1 EXPOSURE

For Objective 1, VTE treatment information will be collected at two time points, baseline and hospital discharge/14 days after baseline, due to the requirement of heparin pre-treatment for some of the studied oral anticoagulants.

On the eCRF page, five oral anticoagulants (vitamin K antagonist, dabigatran, edoxaban, rivaroxaban, and apixaban) are included as pre-specified options, together with three types of heparin pre-treatment (low molecular weight heparin, unfractionated heparin, and fondaparinux) and two types of non-oral therapies (systemic thrombolytic therapy and catheter directed thrombolytic therapy). Patients will be assigned to one of the five oral anticoagulant groups or an additional “Other” group (defined as patients with no oral anticoagulant prescribed), based on the following rules.

Table 6.1: 1 Oral anticoagulant treatment assignment

Treatment at baseline	Treatment at hospital discharge/14 days	Treatment assignment
Vitamin K antagonist ¹	Same as baseline	Vitamin K antagonist
Dabigatran ¹		Dabigatran
Edoxaban ¹		Edoxaban
Rivaroxaban		Rivaroxaban
Apixaban		Apixaban
Heparin pre-treatment without any oral anticoagulant and without non-oral/other therapy	Vitamin K antagonist	Vitamin K antagonist
	Dabigatran	Dabigatran
	Edoxaban	Edoxaban
	Rivaroxaban	Rivaroxaban
	Apixaban	Apixaban
Any of the following without oral anticoagulant: Systemic thrombolytic therapy Catheter directed thrombolytic Other	Same as baseline	Other

¹ Although heparin pre-treatment is required for vitamin K antagonist, dabigatran and edoxaban, these scenarios are included to account for the possibility that these treatments were entered on the baseline eCRF page by the sites due to the retrospective enrollment of patients.

In the event that patients with other combinations of treatment information at baseline and hospital discharge/14 days, such as those listed below, are identified, their treatment assignment should be discussed and determined on a case-by-case basis by the study team during the periodical medical quality review meetings (MQRMs). In the event that a decision

cannot be made due to contradictory information, these inconsistencies should be queried and resolved by the sites.

- More than one oral anticoagulant was entered at a single time point
- A different oral anticoagulant was entered at hospital discharge/14 days than at baseline

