6.7 BASELINE, TIME WINDOWS AND CALCULATED VISITS

The baseline analysis for Objective 2 is cross-sectional in nature. Patients will be assigned to the two treatment groups as described in Section 6.1. For the descriptive analysis, in addition to the data collected at the baseline visit, additional data at hospital discharge or 14 days after the baseline visit (whichever is later) will be collected and summarized descriptively. For the logistic regression analysis to produce estimated propensity scores, data up to the start of dabigatran or VKA treatment will be considered as baseline and will be used as model covariates.

Data from the longitudinal follow-up for collected laboratory data, healthcare resource utilization, and PACT-Q2 will be summarized descriptively at the time points given in [Table 5.3: 2](#). In case time windows will be needed in order to assign observations to visits, observations from 45 days to 134 days after diagnosis will be assigned to month 3, from 135 days to 269 days after diagnosis will be assigned to month 6 and more than 269 days will be assigned to year 1. In case more than one observation is assigned to a certain visit the observation closest to the calculated visit will be assigned. In case two or more observations are on the same day the last will be assigned. Month 3 corresponds to 91 days, month 6 to 182 days, and year 1 to 365 days.

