For the further outcome events such as Recurrent DVT and/or PE, VTE-related mortality, All-cause mortality, Life-threatening bleeding events, Acute coronary syndrome, and Net clinical benefit, incidence rates, KM estimates and KM curves will be calculated for the eligible patients who took the prescribed treatment at least once for both treatment groups. Additionally, above analyses will be performed on the restricted patient set.

Technical specifications

Incidence rates per 100 patient years with 95%-confidence intervals for important outcome events (single and composite outcome) will be calculated the following way. In addition, these analyses will be done stratified by ongoing chronic antiplatelet treatment at baseline. Recurrent events will be disregarded for calculation of incidence rates. Incidence rate λ is defined as

$$\begin{aligned} \text{Incidence rate } \lambda \left[\frac{1}{100} \text{ pt. yrs} \right]: \\ = 100 * \frac{\text{number of patients with event}}{\frac{1}{365.25} * \sum_{\text{patients}} \text{person time at risk(event)}[\text{days}]} \end{aligned}$$

where the denominator is the patient years under risk. The 2-sided 95% CI of λ will be calculated based on the Poisson distribution and its relationship with the Chi-square distribution according to the following formula [7]

$$[\lambda_{\text{lower}}, \lambda_{\text{upper}}] = [\{0.5 \chi^2(\alpha/2; 2x)\}/n, \{0.5 \chi^2(1 - \alpha/2; 2x + 2)\}/n],$$

where $\chi^2(\gamma, r)$ is the 100 γ th the percentile of a chi-square distribution with r degrees of freedom, n is the patient years under risk for the event, x is the number of patients with event, and α for $(1 - \alpha)\%$ 2-sided CIs.

Cumulative risk is defined as cumulative proportion of patients with event and will be calculated as the Kaplan-Meier estimate for failure. The Kaplan-Meier curve will be plotted. The proportion of patients with event, as well as the proportion of censored patients falling into specified intervals and the Kaplan-Meier estimate for failure will be computed for the following categories:

- ≤ 3 months
- $3 <$ and ≤ 6 months
- $6 <$ and ≤ 12 months
- > 12 months

Distribution and overlap of the ePS between the two groups

The ePS is the probability of a patient being in one of the two treatment groups, conditional on relevant observed baseline variables. For this analysis, the ePS for being in the DE group vs. VKA group will be estimated using the multivariable logistic regression model.

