Baseline variables will be included in the model based on their known/suspected association with the main outcome events. As suggested by the literature, only confounders or variables associated with the outcomes will be considered. Table 7.6: 1 summarizes the identified variables to be included in the logistic regression model based on these criteria. In the event of non-convergence, investigations will be done to explore the most likely reason and to aggregate or exclude the responsible variables. Generally, all missing values of variables which will be included in the logistic regression model will be imputed according to Section 6.6.

Table 7.6: 1 Variables for PS model

Variable	Comment	Potential for missing values and implications
Age group	<65, 65 to <75, >=75	Very unlikely
Sex	Male, Female	Rare
BMI	<18.5, 18.5 to <25, 25 to <30, 30 to <35, ≥35, missing	Missing will be imputed
Creatinine clearance	<30, 30 to < 50, 50 to <80, ≥80, missing	Missing will be imputed
Region	Europe, Middle East, North America, Latin America, Asia, Other	Very unlikely
Smoking status	non-smoker, current smoker, past smoker, unknown	Rare – will impute missing and unknown values
Alcohol use	Never, < 1 drink/week, 1-7 drinks/week, ≥8 drinks/week, unknown	Rare – will impute missing and unknown values
Trauma or surgery	True or False (CRF categories, medical history and concomitant diseases will be manually reviewed – 3 month time window)	N/A
Immobilization	True or False (CRF categories, medical history and concomitant diseases will be manually reviewed (past and concomitant))	N/A
Obesity	True or False (CRF categories, medical history and concomitant diseases will be	N/A

	manually reviewed (past and concomitant))	
Thrombophilia	True or False (CRF categories, medical history and concomitant diseases will be manually reviewed (past and concomitant))	N/A
Pregnancy and peri-partum period	True or False (CRF categories, medical history and concomitant diseases will be manually reviewed (3 month time window))	N/A
Concomitant use of aspirin	True or False (concomitant medication and other VTE therapies will be manually reviewed (concomitant))	N/A
Concomitant use of clopidogrel	True or False (concomitant medication and other VTE therapies will be manually reviewed (concomitant))	N/A
Estrogen therapy	True or False (concomitant medication and other VTE therapies will be manually reviewed (3 month time window))	N/A

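### The Objective 2 adjustment models reduce antiplatelet use to aspirin and clopidogrel and omit thrombolysis for the index event, so any imbalance in these recorded treatments that the other covariates miss stays in the bleeding hazard ratio.

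*SAP*

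**What the plan says.** Protocol 9.7.2.1 says the propensity model "considers variables that are risk factors for the occurrence of VTE or bleeding events or affect the choice of anticoagulation treatment". The Objective 2 SAP, Section 7.6, narrows this: "As suggested by the literature, only confounders or variables associated with the outcomes will be considered". Table 7.6: 1 then lists 29 covariates. Three are drug rows: "Concomitant use of aspirin", "Concomitant use of clopidogrel" and estrogen therapy. Table 7.6: 2, for the sensitivity Cox model, lists 14 covariates with the same three drug rows, and it has no row for type of index event.

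The main analysis in Section 7.6 is a Cox model weighted by overlap weights from the Table 7.6: 1 model.

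Other parts of the documents bear on the list:

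- Protocol 7.2 (Treatment Options) counts among the factors that raise bleeding risk "concomitant medications that alter hemostasis (i.e. antiplatelet agents)".
- SAP 7.6 (Technical specifications) says of the incidence rates that "these analyses will be done stratified by ongoing chronic antiplatelet treatment at baseline".
- The Objective 1 SAP, Section 6.1, describes the eCRF as offering "two types of non-oral therapies (systemic thrombolytic therapy and catheter directed thrombolytic therapy)" as pre-specified options.
- Protocol 9.3.1.1 collects every therapy given for the VTE, with dates, and all current concomitant therapies by name and indication.
- The Objective 2 SAP, Section 6.7, says that for the propensity model "data up to the start of dabigatran or VKA treatment will be considered as baseline and will be used as model covariates".

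**The concern.** Overlap weights balance the covariates in the propensity model, and otherwise only what is correlated with them. Neither treatment at issue has a row of its own. An antiplatelet other than aspirin or clopidogrel counts as no antiplatelet use. A patient who received thrombolysis counts the same as one who did not, apart from index event type (DVT, PE or both) and general history. Index event type does not grade severity. Location, extent and severity of the thrombus are collected under Protocol 9.3.1.1, but they are not modelled either, so no other row stands in directly for the severity that thrombolysis may mark.

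If either treatment is more common in one arm and is associated with bleeding, the difference passes into the hazard ratio for major and clinically relevant non-major bleeding. The sensitivity Cox model has the same gap, so agreement between the two analyses would give no reassurance on this point.

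**Working it through.** **1. The list against the plan's own rules**

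| Treatment | Basis for inclusion | Recorded before DE/VKA start? | Table 7.6: 1 | Table 7.6: 2 |
|---|---|---|---|---|
| Aspirin, clopidogrel | Protocol 7.2, antiplatelet class | Yes | In | In |
| Other antiplatelets | Protocol 7.2, same class; SAP 7.6 stratification | Yes, concomitant therapies by name | Out | Out |
| Thrombolysis for the index event | Association with bleeding and with drug choice is assumed; the documents do not state it | Yes, VTE treatment with dates; eCRF options as described in the Objective 1 SAP | Out | Out |

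The aspirin and clopidogrel rows are themselves to be derived by manual review of concomitant medication and other VTE therapies. The records that would identify the omitted treatments are thus already being read.

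**2. The plan's own figure**

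No figure is in dispute. The design hazard ratio of 0.69 (Protocol 9.5) serves only as a yardstick. Freedman events at that ratio are (1.960 + 1.282)² × (1.69/0.31)² = 10.51 × 29.72 ≈ 313. With 15% exponential loss over one year, 5000 patients yield about 302 events and 89.0% power. At an unrounded 0.6852 the power is 90%. The stated 5000 is reproduced.

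**3. Size of a possible shift**

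The documents give no prevalence or bleeding effect for the omitted treatments, so every input here is an assumption. For an omitted yes/no treatment with prevalence p in each arm and bleeding ratio R, the observed hazard ratio is multiplied by

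[1 + p_DE(R − 1)] / [1 + p_VKA(R − 1)].

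The last column applies the SAP 7.6 standardized difference for a dichotomous variable, d = (difference in proportions) / √{[p_DE(1 − p_DE) + p_VKA(1 − p_VKA)]/2}, in absolute value.

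| p_DE | p_VKA | R | Factor | True 0.69 seen as | d |
|---|---|---|---|---|---|
| 2% | 4% | 2 | 1.02/1.04 = 0.981 | 0.677 | 0.12 |
| 2% | 6% | 2 | 1.02/1.06 = 0.962 | 0.664 | 0.21 |
| 5% | 10% | 2 | 1.05/1.10 = 0.955 | 0.659 | 0.19 |
| 2% | 6% | 3 | 1.04/1.12 = 0.929 | 0.641 | 0.21 |
| 5% | 10% | 3 | 1.10/1.20 = 0.917 | 0.633 | 0.19 |
| 1% | 6% | 3 | 1.02/1.12 = 0.911 | 0.628 | 0.27 |

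The factors run from 0.91 to 0.98. With the arms swapped they run from 1.02 to 1.10 (1.04/1.02 and 1.12/1.02). A far larger assumed gap, 10% against 20% with R = 3, gives 1.20/1.40 = 0.857 with d = 0.28. That would need one VKA patient in five to receive a treatment not already modelled.

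**4. Could this alone produce the design effect?**

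Set the factor to 0.69 with R = 3 and solve p_VKA = [(1 + 2p_DE)/0.69 − 1]/2. For p_DE = 2% this gives (1.04/0.69 − 1)/2 = 25%. For p_DE = 10% it gives (1.20/0.69 − 1)/2 = 37%. Gaps of that size are not a realistic worry.

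**5. Would the balance check catch it?**

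SAP 7.6 considers re-estimating the model only when an adjusted standardized difference exceeds 0.25. Five of the six tabulated scenarios fall below that, so a residual imbalance of that size would pass even if the variable were displayed. Displaying the variables is useful, but it does not replace modelling them.

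**The case against.** The strongest reply is that the list is already broad. With 29 covariates it includes major bleeding history, prior gastrointestinal bleed, renal and hepatic disease, cancer, heart failure, region and index event type. These will absorb part of any imbalance, and the bias formula ignores that. This stands, and it makes the figures above upper-end illustrations for their inputs. A reader might infer from the gap that the model as a whole adjusts for two drugs only. It does not; the gap concerns drugs that affect bleeding.

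The formula also holds R constant over the year, while follow-up starts at DE or VKA initiation (SAP 6.1). An acute treatment given before then need not double or triple bleeding for twelve months. This also stands, so R = 3 for thrombolysis is a high assumption.

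Confounding further requires the arms to differ, and no document shows that they do. A reader might infer that the plan favours dabigatran. Nothing in the documents supports a direction.

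It is tempting to add NSAIDs and multiply several biases into one larger figure. The documents never name NSAIDs, and their capture depends on entry as a concomitant therapy, so they do not carry the point.

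Nor can one say that an imbalance would go unseen. SAP 7.6 checks balance for covariates of interest without defining that set, and SAP 7.2 tabulates concomitant medication by preferred name. A crude imbalance in named antiplatelets might well be visible there, though unweighted.

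Two defences do not answer the point. The antiplatelet-stratified incidence rates are descriptive: they leave the hazard ratio unadjusted and do not address thrombolysis. The protocol's acknowledgement of residual unmeasured confounding (9.9) does not cover variables that are recorded and then left out. SAP Sections 5.3, 6.4 and 7.7 are not in the available text and may hold relevant subgroups, but subgroups would not change the covariates in the main model.

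**Conclusion.** The omission is established from the two covariate tables. It is clearest for antiplatelets, where the protocol names the class, the SAP already uses a class-level variable for crude rates, and the adjusted analysis falls back to two named drugs. For thrombolysis the data are recorded in time to be used, but the link to bleeding and to drug choice is an assumption that the documents do not supply.

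Whether the hazard ratio is biased is unknown. Assuming R of 2 to 3 and prevalence gaps of 2 to 5 percentage points, the shift is about 2% to 10% in either direction, before allowing for what the other covariates absorb. That is too small to create the design effect of 0.69, but it could change how a modest hazard ratio is read. The comparison is declared exploratory (Protocol 9.7.1), yet it serves one of the two primary objectives. The change is worth making, but the gap does not invalidate the analysis.

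**What to change.** In Tables 7.6: 1 and 7.6: 2:

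- Replace the clopidogrel row with any antiplatelet other than aspirin (yes/no).
- Add systemic or catheter-directed thrombolysis for the index event before DE/VKA start (yes/no).
- Show both in the unweighted and weighted balance table, and state which variables count as covariates of interest.

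NSAID use, where entered as a concomitant therapy, can go into a sensitivity model. Because the SEAP is marked final (29-May-19), record the change as an amendment. If the comparison has already been run, report it as an added sensitivity analysis.

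The cost is SAP wording and two binary variables coded during the manual review already planned. Each table grows by one row, from 29 to 30 and from 14 to 15. No new data are needed. If the new terms separate the arms, some effective sample size is lost. If a term is too sparse for the model to converge, it can be aggregated or dropped, as SAP 7.6 already allows.

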where \hat{p}_{DE} and \hat{p}_{VKA} denote the proportion or mean of the dichotomous variables in DE and VKA patients, respectively. This approach described above will be repeated for the same covariates of interest after applying the appropriate overlap weight to each patient based on the ePS and will be presented for each covariate. Note that after weighting, the mean will be used instead of the proportion for binary and categorical variables because the weighting applied will make the variables continuous. After weights will have been applied sample means and variances will be substituted by weighted means and weighted sample variances denoted by

$$\bar{x}_{\text{weight}} = \frac{\sum O_i x_i}{\sum O_i}$$

and

$$s^2_{\text{weight}} = \frac{\sum O_i}{(\sum O_i)^2 - \sum O_i^2} * \sum O_i (x_i - \bar{x}_{\text{weight}})^2$$

where O_i is the weight assigned to the i-th patient.

These unadjusted (i.e., prior to using the overlap weights with ePS adjustment) and adjusted (using overlap weights) standardized differences for the mean will be presented for each covariate.

Balance will then be assessed to determine whether the weighted covariates procedure produces standardized differences for the mean and SD closer to zero (indicating a better balance between the study cohorts) than those of unadjusted covariates. Adjusted standardized differences for any covariate that are greater than 0.25 will potentially warrant re-estimation of the ePS model to improve balance.

- 2.) Sensitivity analysis of the main outcomes (Major bleeding and clinically relevant non major bleeding, and symptomatic recurrent VTE including VTE-related mortality)
 - a.) As sensitivity analysis for the comparison of the two treatment groups, dabigatran etexilate and VKA, with regards to the main outcomes a multivariable Cox regression model will be performed. The multivariable Cox regression model will include the variables given in [Table 7.6: 2](#). In case of model convergence issues due to limited number of events, some variables may be removed from the model as deemed necessary.

Table 7.6: 2 Variables for Cox regression model

Variable	Comment	Potential for missing values and implications
Age	continuous	Very unlikely
BMI	continuous	Missing will be imputed
Trauma or surgery	True or False (CRF categories, medical history and concomitant diseases will be manually reviewed – 3 month time window)	N/A

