Immobilization	True or False (CRF categories, medical history and concomitant diseases will be manually reviewed (past and concomitant))	N/A
Thrombophilia	True or False (CRF categories, medical history and concomitant diseases will be manually reviewed (past and concomitant))	N/A
Pregnancy and peri-partum period	True or False (CRF categories, medical history and concomitant diseases will be manually reviewed (3 month time window))	N/A

Concomitant use of aspirin	True or False (concomitant medication and other VTE therapies will be manually reviewed (concomitant))	N/A
Concomitant use of clopidogrel	True or False (concomitant medication and other VTE therapies will be manually reviewed (concomitant))	N/A
Estrogen therapy	True or False (concomitant medication and other VTE therapies will be manually reviewed (3 month time window))	N/A
Concomitant cancer	True or False (CRF categories, medical history and concomitant diseases will be manually reviewed (concomitant))	N/A
Hypertension	True or False (CRF categories, medical history and concomitant diseases will be manually reviewed (concomitant))	N/A
History of previous VTE	True or False (CRF categories, medical history and concomitant diseases will be manually reviewed (regardless of timing))	N/A
History of major bleeding or prior gastrointestinal bleed	True or False (medical history and concomitant diseases will be manually reviewed (regardless of timing))	N/A
Chronic renal disease	True or False (CRF categories, medical history and concomitant diseases will be manually reviewed (concomitant))	N/A

Patients who complete the planned anticoagulation treatment prior to one year or discontinue initial anticoagulation treatment permanently will be censored at date of last drug intake + 6 days for both dabigatran etexilate and VKA or at first intake of another relevant anticoagulation treatment, whichever occurs first. A patient is considered to have permanently stopped initial anticoagulation treatment if other relevant anticoagulation treatment is initiated or if treatment has been interrupted for more than 30 days.

Multiple imputation methods (e.g. the fully conditional specification method) will be used to impute both continuous and categorical variables appropriately with arbitrary missing patterns.

- b.) In addition, Cox regression analysis (based on the main analysis model) will be performed without censoring at permanent discontinuation (intention to treat (ITT) approach).

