7.9.2 Laboratory data

The following laboratory variables at the described time points (Table 5.3:) will be summarized descriptively.

Table 7.9.2: 1 Laboratory Variables

Parameter	Unit
Serum Creatinine	mg/dL
Hemoglobin	g/L
International Normalized Ratio (INR)	

Creatinine Clearance	mL/min
----------------------	--------

Creatinine clearance (mL/min) will be derived based on the collected serum creatinine data using the Cockcroft-Gault formula [55].

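### The main-analysis propensity model uses age, BMI and creatinine clearance only in bands, so confounding inside the bands can remain and the band-level balance check cannot show it

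*SAP*

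**What the plan says.** Objective 2 SAP, Section 7.6, selects the covariates for the score on outcome grounds: "Baseline variables will be included in the model based on their known/suspected association with the main outcome events". It adds that "Table 7.6: 1 summarizes the identified variables to be included in the logistic regression model based on these criteria". That table then fixes their form:

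- Age: "<65, 65 to <75, >=75". With the entry age of 18 (Protocol 9.2.1), the first band runs from 18 to 64 years; the last is open-ended.
- BMI: "<18.5, 18.5 to <25, 25 to <30, 30 to <35", plus a top band from 35.
- Creatinine clearance: "<30, 30 to < 50, 50 to <80", plus a top band from 80.

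Obesity and chronic renal disease also enter, as true/false flags. No continuous term, spline or interaction is given. The main analysis is a Cox model with overlap weights from this score, and no further covariates are stated.

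Continuous values are available. Section 7.9.2 states: "Creatinine clearance (mL/min) will be derived based on the collected serum creatinine data using the Cockcroft-Gault formula". The table headed "Table 7.6: 2 Variables for Cox regression model", used for sensitivity analysis 2a, takes age and BMI as continuous. It has no clearance term, only the chronic renal disease flag.

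For balance, Section 7.6 assesses multi-category variables as one dummy per category. It also gives a formula for continuous variables, but the visible text does not say which form is used for age, BMI and clearance. Adjusted standardized differences above 0.25 may lead to re-estimation of the score.

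**The concern.** A propensity score can remove only the differences that its terms describe. A 20-year-old and a 60-year-old get the same age contribution, as do patients with clearance of 85 and 140 mL/min. If the choice between dabigatran and VKA varies with age or clearance inside a band, and risk does too, the main hazard ratio keeps that part of the confounding.

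The documents make this relevant. Protocol 7.2 lists chronic renal disease among the conditions that raise bleeding risk. Its background also cites gastrointestinal bleeding thresholds of 75 years in women and 85 in men (another indication), and 85 lies inside the top age band. Protocol 9.9 names channelling as a possible bias and relies on propensity methods to address it.

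Band-level balance would look excellent whether or not the problem is present.

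**Working it through.** **Why the bands balance almost automatically.** For a logistic model with treatment indicator Z (1 = DE), fitted score P and any term x in the model, the likelihood equations give Σ(Z − P)x = 0. Splitting by group, Σ over DE of (1 − P)x = Σ over VKA of P·x. The SAP weights are exactly 1 − P for DE and P for VKA. With the intercept, the sums of weights are equal too, so the weighted means of every modelled dummy are equal. Averaging the score over imputations and then trimming makes this approximate. Nothing in the equations constrains a within-band mean.

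**Simulation.** The documents state no figure to reproduce, and the channelling and hazards below are assumptions.

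- 400 cohorts of 5,000 in each of 10 settings; true hazard ratio 1.00; about 300 events. For comparison, Protocol Table 9.5:2 implies 5,000 × (5.3% + 7.7%)/2 = 325 events, or 276 after × 0.85 for loss.
- Age mean 61, SD 16, range 18 to 95; Cockcroft-Gault clearance; 10% of BMI and 15% of clearance missing; 5 imputations; mean score; trimming to the shared range.
- 23 of the 26 other Table 7.6: 1 variables in the model (pregnancy, antiphospholipid syndrome and polycythemia left out as rare).
- Weighted d by the SAP formulas; weighted Cox model.

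The first column gives slopes per year of age / per 30 mL/min of clearance: log-odds of DE, then log-hazard.

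| Smooth setting | Raw age d | Weighted age d | Weighted clearance d | HR, bands | HR, bands + continuous | HR, sensitivity Cox 2a |
|---|---|---|---|---|---|---|
| −0.015/0; 0.02/0 | 0.23 | 0.06 | 0.03 | 0.990 | 1.003 | 1.003 |
| −0.03/0; 0.03/0 | 0.45 | 0.12 | 0.06 | 0.974 | 1.010 | 1.010 |
| −0.015/0.15; 0.02/−0.15 | 0.35 | 0.08 | 0.10 | 0.976 | 1.003 | 0.989 |
| −0.03/0.3; 0.03/−0.2 | 0.65 | 0.16 | 0.20 | 0.947 | 1.011 | 0.977 |
| −0.045/0.3; 0.03/−0.2 | 0.84 | 0.22 | 0.22 | 0.931 | 1.010 | 0.975 |

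The Monte Carlo SE of log HR is about 0.006, so the bands-plus-continuous results lie within two SEs of 1.00.

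*Bias against the truth*, ln(HR): −0.010, −0.026, −0.024, −0.054, −0.071. With SD(log HR) of 0.12 to 0.13, this is roughly 0.1 to 0.6 SD.

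*Paired difference*, bands minus bands plus continuous, in log HR: −0.013, −0.036, −0.027, −0.065, −0.081 (SE 0.001 or less), or 0.11 to 0.62 SD.

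Other settings:

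- Prescribing steps at the SAP cut-points (raw age d 0.31, 0.59): banded HR 0.997 and 1.002, so no bias.
- Steps at other cut-points (age 70 and 80, clearance 60; raw age d 0.45): 0.968 against 0.994, although weighted age d was only 0.03 and clearance d 0.01.
- BMI-only channelling (raw BMI d 0.31): weighted BMI d 0.04, log-HR shift 0.005.
- Reversed channelling: 1.063 against 1.000, so the sign is not fixed.

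Across all 4,000 datasets the largest d on any band with the banded model was 0.058.

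**Second check.** This used 400,000 patients, no missing data and different assumed distributions. With log-odds and log-hazard slopes per SD of age and of clearance of 0.2 and 0.2, 0.4 and 0.3, and 0.8 and 0.5, banded weighting gave rate ratios of 0.978, 0.946 and 0.861 (unweighted 0.893, 0.728 and 0.419). Band d was below 1e-14, and continuous d was about 0.07, 0.14 and 0.27. Adding linear terms gave 0.999 to 1.001 in every scenario. With no effect of these variables on outcome, the banded ratio was 1.000.

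**The case against.** **Other terms in the score.** Obesity, chronic renal disease, hypertension, heart failure, cancer and similar flags may track age or renal function and so absorb part of the within-band difference. This stands in part. With 300,000 patients per setting, eight age-correlated flags gave 0.990, 0.982, 0.951 and 0.943, against 0.984, 0.968, 0.923 and 0.906 with independent flags: a log shift about 40% smaller. A further check with a renal-disease flag in the score gave 0.945 to 0.986 with correlated flags and 0.940 to 0.984 with independent ones. Both became 0.999 to 1.000 once continuous terms with squares were added. The flags shrink the bias by an amount that depends on assumptions; they do not remove it. The table's sizes would be too large if real covariates carry more information on age than the simulated ones did.

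**Size.** No document supports a particular strength of channelling, and hazard ratios of 0.947 and 0.931 need raw age differences of 0.65 and 0.84. That is fair. In the three weaker smooth settings the bias is 0.010 to 0.026 on the log scale. Risk must also vary within bands, and prescribing must depend on these variables at all. BMI matters little.

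**Existing safeguards.** The SAP's formula for continuous variables, and its mention of mean and SD, suggest that continuous balance may be checked; the covariate list may sit in sections not public. Even so, every smooth setting in the table stays below the 0.25 trigger. Sensitivity analysis 2a removes the age part and about half or more of the combined shift (0.976 to 0.989, 0.947 to 0.977, 0.931 to 0.975), but not all of the clearance part, and it does not correct the main estimate.

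**Exploratory status.** Protocol 9.7.1 calls the analyses descriptive. This lowers the stakes but does not justify an avoidable bias.

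**Conclusion.** The concern holds. The main-analysis score has no term that can remove a within-band difference in age, BMI or clearance, and near-zero differences on the bands are not evidence that none exists. The bands do most of the work: about three quarters of the raw age gap is removed under smooth channelling. What remains is systematic. Under the main simulation's assumptions it moves a true hazard ratio of 1.00 to between 0.990 and 0.931, or above 1 if channelling runs the other way. It is negligible if prescribing follows the SAP's cut-points or if risk is flat within bands.

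The mechanism is certain. The size is not, because the documents give no distribution of age or clearance by treatment. This is an inexpensive improvement that should be made, not a defect that invalidates the analysis.

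**What to change.** In Table 7.6: 1, keep the bands and add age, BMI and creatinine clearance as continuous terms with squares (or splines). State that weighted standardized differences are reported on the continuous values as well as on the bands; if the non-public sections already say so, nothing changes there.

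Add rather than replace. When prescribing followed the SAP cut-points, replacing the bands left a largest band d of 0.06 to 0.09 on average, against 0.01 to 0.02 with bands plus continuous terms.

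Optional: a balance threshold tighter than 0.25, and a re-fit of the score after trimming.

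Cost: SAP wording and six model terms (three linear, three squared). The values are already collected or derived. Section 7.6 foresees methods that "will be used to impute both continuous and categorical variables appropriately with arbitrary missing patterns", but it says so under the sensitivity Cox model. Section 6.6 should therefore say that BMI and clearance are imputed as continuous for the score too, with the bands derived from the imputed values. Effective sample size fell from 4,856 to 4,834 (0.5%) in the weakest smooth setting, from 4,279 to 4,087 (4.5%) in the strongest, and by 0.1% when prescribing followed the SAP cut-points.
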